#### 2. Data source

Retrospective case note data is collected on paper case report forms (CRFs) before upload onto an electronic data management system by the European coordinator.

## 2.1 Selection of case and controls (total possible to be recruited)

		Location	of participant a sample	at time of
Diagnostic categories:		Hospital	Community	TOTAL
CDI positive cases	1. CCNA positive	83	20	103
	2. CCNA negative/Simoa positive	49	22	71
	3. CCNA and Simoa negative but CTC positive or bioFire pos	24	15	39
CDI negative controls	4. Negative control *	365	147	512
Total number selected for case/control study 521 204		725		

Table1. The total number of samples selected for the case/control study (n=725). The table shows the number of CDI positive cases according to the indicated diagnostic categories (1-3, n=213) and by location of participant (Hospital n=156, Community n=57). Negative controls (4, n=512) were selected at a rate of 1:3 from matching participating sites (one case to three controls). As some participating sites had less than 3 controls per case, average rate was of 1:2.4 (one case to 2.4 controls) (\*).

#### 2.3 Data to be collected

A clinical report form will be completed for each patient following collection of the patient notes. For a full list of variables please see attached table in appendix 1.

#### 2.4 Timeline

Sample collection period: Summer/Winter 2018 CRF collection period ends: June 2019 Data upload and verification: June 2019 Analysis and Write up: September 2019

#### 2.5. Analysis objectives

The main objectives of the analyses are to;

- 1. Determine the outcomes of cases (of each classification) vs controls, and compare between countries and hospital vs community cases
- 2. Determine the risk factors for cases (of each classification) vs controls, and compare between countries and hospital vs community cases

#### 3. Sample size

Based on a previous risk factor study using a similar study design (ORCHID) the following power calculations were made;

Age >65; previously found 65% in cases and 39% in controls. Comparing proportions for equivalence, a sample size of 20 cases and 60 controls would give 80% power to detect a difference of 23% between cases and controls with an  $\alpha$  type one error rate of 5%.

At least one antibiotic; previously found 67% in cases and 45% in controls. Comparing proportions for equivalence, a sample size of 23 cases and 67 controls would give and 80% to detect a difference of 22% between cases and controls with an  $\alpha$  type one error rate of 5%.

At least one antibiotic; alternative single centre cohort found 85% in cases and 75% in controls. Comparing proportions for equivalence, a sample size of 92 cases and 276 controls would give and 80% to detect a difference of 13% between cases and controls with an  $\alpha$  type one error rate of 5%.

Previous surgery; previously found 26% in cases and 16% in controls. Comparing proportions for equivalence, a sample size of 156 cases and 469 controls would give and 80% to detect a difference of 10% between cases and controls with an  $\alpha$  type one error rate of 5%.

Previous surgery; alternative single centre cohort previously found 41% in cases and 28% in controls. Comparing proportions for equivalence, a sample size of 88 cases and 351controls would give and 80% to detect a difference of 13% between cases and controls with an  $\alpha$  type one error rate of 5%.

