#### 4. Study Design

This is case-control study with the cases and controls selected from the patients who had stool samples tested for CDI. The study will collect data on cases/controls (1:3 ratio) identified during the sample collection phase of COMBACTE-CDI.

For each case of confirmed CDI (or other diagnostic criteria), three controls will be randomly selected from the same participating site (i.e. if hospital case, controls will come from the same hospital, if community case, controls will come from the community). Thus initially the controls are only matched on location only, as the cohort is not large enough to enable closer matching. Subsequent further matching (e.g. by age) may be considered depending on final available sample size, but this would reduce the overall pool of controls substantially.

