#### 7.2 Univariate analysis

Univariate analysis will be used to assess outcomes and risk factors; continuous variables will be compared between cases and controls by t-test; categorical variables will be compared between cases and controls by chi-squared (fishers exact where numbers are below 5). Risk ratios (Odds ratio if it is case control study) will be calculated for CDI cases with identified variables of interest. Univariate analysis will be used to assess consistency between countries and between different healthcare settings.

The variables to be included in the univariate analysis are shown in the table in appendix 1.

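### Three of the five 80% power statements in SAP section 3 do not hold (43–53%, 44% and 65% two-sided), so the section overstates what the by-class comparisons can detect for the smaller effects

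*SAP*

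**What the plan says.** SAP section 3 takes prevalences from earlier work and gives five sample sizes, each said to give 80% power at a 5% type I error rate. Sidedness is not stated. Each is introduced as an equivalence comparison but ends as detection of a difference.

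- Age over 65: "previously found 65% in cases and 39% in controls"; then "a sample size of 20 cases and 60 controls would give 80% power to detect a difference of 23% between cases and controls".
- At least one antibiotic, 67% v 45%: "a sample size of 23 cases and 67 controls would give and 80% to detect a difference of 22" percent.
- At least one antibiotic, second source: "alternative single centre cohort found 85% in cases and 75% in controls"; then "a sample size of 92 cases and 276 controls would give and 80% to detect a difference of 13" percent.
- Previous surgery, 26% v 16%: 156 cases and 469 controls, for 10 points.
- Previous surgery, second source, 41% v 28%: "a sample size of 88 cases and 351controls would give and 80% to detect a difference of 13" percent.

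On the design, SAP section 4 says: "The study will collect data on cases/controls (1:3 ratio) identified". On the test, SAP section 7.2 says: "categorical variables will be compared between cases and controls by chi-squared (fishers exact where numbers are below 5". SAP section 2.5 makes outcomes and risk factors for cases of each classification against controls the main objectives. Table 1 in SAP section 2.1 lists 103, 71 and 39 cases in three classes (213 in all) and 512 controls.

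Protocol 3.1.5 expects 1,620 samples per sampling day at 10% toxin positivity and derives 240 positives. Protocol 3.2.5 and 3.3.5 carry this forward as 480 over two days.

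**The concern.** Section 3 is the SAP's only sample-size basis. Some of its numbers look too small for the effects quoted: 20 cases and 60 controls is a small study for a gap of about a quarter. Two statements pair a set of rates with a difference that is not their gap. The last uses 88/351, about 1:4, although the design is 1:3.

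Recruitment does not depend on this, since Table 1 gives the total possible. Interpretation does. A reader who compares the class sizes in Table 1 with the needs stated in section 3 may conclude that a class is large enough when it is not, and may read a non-significant result there as absence of association. SAP section 4.2 warns of small numbers only within countries.

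**Working it through.** **Inputs.** Rates, group sizes and the 5% error rate are from SAP section 3. Class sizes are from Table 1, taken as mutually exclusive. Two-sided testing is my assumption, consistent with the chi-squared test; one-sided results are also shown.

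**Formula.** With p̄ = (n1·p1 + n2·p2)/(n1 + n2),
SE0 = √[p̄(1−p̄)(1/n1 + 1/n2)],
SE1 = √[p1(1−p1)/n1 + p2(1−p2)/n2],
power = Φ[(|p1−p2| − 1.96·SE0)/SE1].

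**Attempt to reproduce the stated 80%.**

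Age, 20/60, 65% v 39%: p̄ = (13 + 23.4)/80 = 0.455; SE0 = 0.1286; SE1 = 0.1239; (0.26 − 0.2521)/0.1239 = 0.06; power 53%.

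Surgery, second source, 88/351: p̄ = 134.36/439 = 0.306; SE0 = 0.0549; SE1 = 0.0576; (0.13 − 0.1076)/0.0576 = 0.39; power 65%.

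| Statement | n | Two-sided 5% | One-sided 5% |
|---|---|---|---|
| Age | 20/60 | 53% at 26 points; 43% at 23 | 56–67% |
| Antibiotic | 23/67 | 44% | 57–59% |
| Antibiotic, second source | 92/276 | 73–78% at 13 points; 51% at 10 | – |
| Surgery | 156/469 | 78% | – |
| Surgery, second source | 88/351 | 65% (62% at 1:3, 88/264) | 75% |

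Exact enumeration of the chi-squared test agrees with the two-sided figures within 0.01. The one-sided ranges cover the pooled and exact methods and, for age, both differences. Unpooled, arcsine, continuity-corrected and two one-sided equivalence calculations were also tried; none gives 80% for age, antibiotic and surgery (second source) together.

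**Gaps.** 65 − 39 = 26, stated 23. 85 − 75 = 10, stated 13. The other three match.

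**Cases needed at 1:3 for 80%.** n1 = [1.96√(p̄(1−p̄)·4/3) + 0.842√(p1(1−p1) + p2(1−p2)/3)]²/(p1−p2)², with p̄ = (p1 + 3·p2)/4. At the quoted rates, in the order of the table: 37.5, 52.6, 172.1, 166.1 and 136.2, so 38, 53, 173, 167 and 137. The SAP has 20, 23, 92, 156 and 88. Age at 23 points needs 49; the second antibiotic statement at 13 points needs 97–108.

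**Power with the actual counts against 512 controls, before exclusions.**

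| Effect | 213 (pooled) | 103 | 71 | 39 |
|---|---|---|---|---|
| Age, 23–26 points | >99% | ≥99% | ≥96% | 81–90% |
| Antibiotic 67 v 45 | >99% | 99% | 94% | 77% |
| Antibiotic 85 v 75 | 86% | 60% | 45% | 26% |
| Same, at 13 points | – | 82–87% | 67–72% | 40–43% |
| Surgery 26 v 16 | 86% | 66% | 55% | 38% |
| Surgery 41 v 28 | 92% | 73.5% | 61% | 41% |

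Check for 103 v 512 at 41 v 28: SE0 = 0.0496; SE1 = 0.0524; (0.13 − 0.0972)/0.0524 = 0.63; power 0.735.

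**Protocol.** 1,620 × 0.10 = 162 per day; 2 × 162 = 324. The stated 480 is 480/324 = 1.48 times that.

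**The case against.** The strongest reply is that these errors change little. Recruitment is complete, section 3 never claims to power each class, no SAP rule treats a non-significant result as evidence of no association, and the pooled comparison has ample power. All of that is true, and it limits the point to a correction of the text and of how by-class results are read.

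Several stronger readings are tempting and not supported:

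- That the study as a whole is underpowered. Pooled power is at least 86% for every quoted effect before exclusions. The age effect keeps at least 81% in every class, and antibiotic 67 v 45 has 94% or more with 71 or 103 cases.
- That the 103 CCNA-positive cases meet the stated need of 92 yet have only 60%. The SAP ties 92/276 to 13 points, where 103 cases have 82–87%. The 60% applies only if 10 points is meant, and the documents do not settle that.
- That the 39-case class is misjudged for antibiotic 67 v 45. Its 77% is as close to 80% as the 78% for surgery 156/469, which is near enough.
- That 23 against 26 points must be an error. A target below the observed gap can be a deliberate, conservative choice. Powering for 13 points when 10 were observed runs in the favourable direction and needs an explanation.
- That the 480 in the protocol shows a recruitment failure. Protocol 3.1.5 says the number cannot be predicted accurately, and the SAP replaces the forecast with the 213 cases found.

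**Conclusion.** The point holds as a correction. Three of five power statements are wrong by a wide margin, on either sidedness. A fourth (92/276) is near 80% only at a difference that its own rates do not show. The fifth (156/469) is acceptable. The equivalence wording conflicts both with the stated aim of detecting a difference and with the planned test.

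The practical consequence is confined to the smaller effects in the by-class comparisons. The clearest case is 41% v 28%: 103 cases exceed the stated need of 88 but have 73.5%. Across the two surgery effects, power is 66–73.5%, 55–61% and 38–41% in the three classes.

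These figures are unadjusted, combine all ages, assume that the quoted rates hold in each class and use all 512 controls. They are best cases, because SAP section 4.1.5 removes some controls after the CRF is received and section 5 drops patients with a missing outcome from that outcome's analysis. The protocol counts are a minor correction of the record.

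**What to change.** In SAP section 3:

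1. Replace the equivalence wording with a two-sided 5% test of difference.
2. Reconcile 13 with 10 points against the source, and explain or reconcile 23 with 26.
3. Restate either the actual power or the cases needed at 1:3, using the figures derived above for whichever differences are confirmed.
4. Add power or detectable differences by class for the Table 1 counts. At 16% control prevalence and 80% power these are about 12, 14 and 19 points for 103, 71 and 39 cases against 512 controls, to be labelled as before exclusions.

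In protocol 3.1.5, 3.2.5 and 3.3.5, make inputs and counts agree: 162 per day and 324 over two days, or corrected inputs.

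The cost is text only, with no extra patients and no change to the analysis. The stated figures become less favourable.

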#### 4. Study Design

This is case-control study with the cases and controls selected from the patients who had stool samples tested for CDI. The study will collect data on cases/controls (1:3 ratio) identified during the sample collection phase of COMBACTE-CDI.

For each case of confirmed CDI (or other diagnostic criteria), three controls will be randomly selected from the same participating site (i.e. if hospital case, controls will come from the same hospital, if community case, controls will come from the community). Thus initially the controls are only matched on location only, as the cohort is not large enough to enable closer matching. Subsequent further matching (e.g. by age) may be considered depending on final available sample size, but this would reduce the overall pool of controls substantially.

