## 6.3. Study period and important time points.

The study period is June 2018-June 2019.

The index date for the cases is defined as the date of the stool sample collection (either June/July 2018 or Oct/Nov 2019).

The index date for the controls is defined as the date of the stool sample collection either June/July 2018 or Oct/Nov 2019).

Queries within the CRF relate to that patients episode, with reference to the six months prior and six months subsequent to the index sample.

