#### 7.3 Regression analysis (or Multivariate analysis)

To evaluate risk factors considering confounding, unconditional logistic regression analysis will be perform with case/control as dependent variable, and all variables listed in the univariate analysis as independent variables.

To build the logistic regression model, we will apply a stepwise forward selection to identity risk factors. The process of the forward selection will be recorded to rank the risk factor.

The regression analysis will be performed separately for the three age groups (18-49,50-64 and 65+ years). If there is a reasonable sample size analysis will also be performed for the age group <18 years.

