# Appendix 1. Variable description table

Item	Data Item	Definition	Analysis type	Time window
Number		of variable		
	Study ID			
1. Patient	Demographics	1	Γ	
1.1	Age of patient at time of sample	Continuous	Univariate/multivariate	Patient admission when the sample was taken
1.2	Gender of patient	Binary	Univariate/multivariate	Patient admission when the sample was taken
1.3	Date of sample in COMBACTE	N/A		
1.4	Location of the patient at time of sample	Categorical	Univariate/multivariate	Patient admission when the sample was taken
2. Admissi	on History	1	1	
2.1	If the sample was taken as a hospital inpatient Reason for admission	Categorical	Univariate/multivariate	Patient admission when the sample was taken
2.1.1	Date of admission	Number of days between admission and index sample is Continuous	Univariate/multivariate	Patient admission when the sample was taken
2.1.2	Admitting specialty	Categorical Patient admission when the sample was taken	Univariate/multivariate	Patient admission when the sample was taken
2.2	Did the patient move wards during their admission	Categorical	Univariate/multivariate	Patient admission when the sample was taken
2.2.1	If yes, please complete the table	Number of days between admission and movement is	Univariate/multivariate	Patient admission when the sample was taken

		Continuous		
2.3	If the sample was taken as a hospital inpatient Where was patient	Categorical	Univariate/multivariate	Patient admission when the sample was taken
	admitted from			
2.4	If the sample was taken as a hospital inpatient Where was the patient discharged to	Categorical	Univariate/multivariate	Patient admission when the sample was taken
2.5	If the sample was taken in the community patient Reason for GP appointment	Categorical	Univariate/multivariate	Patient admission when the sample was taken
2.6	Did the patient have contact with a healthcare facility 6 months prior to the sample being taken?	Binary	Univariate/multivariate	Up to 6 months previous to sample
2.6.1	If yes and the visit was >24 hours, please complete the table below	Categorical	Univariate/multivariate	Up to 6 months previous to sample
2.6.2	If yes, because the patient had regular outpatient appointments, please complete the table below Frequency of visits - nature of visits	Categorical	Univariate/multivariate	Up to 6 months previous to sample

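### Sampling round (June/July v Oct/Nov) is neither a matching factor nor a covariate, so the case-control odds ratios are open to confounding by round, conditional and probably modest; forcing in one binary term would deal with it

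*SAP*

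**What the plan says.** SAP 2.4 gives the collection as "Sample collection period: Summer/Winter 2018". SAP 6.3 places the samples in two windows: "The index date for the cases is defined as the date of the stool sample collection (either June/July 2018 or Oct/Nov 2019". The same wording is used for controls.

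SAP section 4 takes controls from the case's own site and setting: "three controls will be randomly selected from the same participating site". It adds: "Thus initially the controls are only matched on location only, as the cohort is not large enough to enable closer matching". Age is the only example given of possible later matching. SAP 2.1, Table 1, shows the selection already made: 213 cases and 512 controls.

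In SAP Appendix 1, item 1.3 ("Date of sample in COMBACTE") has N/A as its definition and no analysis type. SAP 7.2 takes its list from that table ("The variables to be included in the univariate analysis are shown in the table in appendix 1"). SAP 7.3 then enters "all variables listed in the univariate analysis as independent variables" into an unconditional logistic regression, and states: "we will apply a stepwise forward selection to identity risk factors". No design term is named as forced in.

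**The concern.** Under the stated rule, the controls' split between rounds follows each site's negative samples, and the cases' split follows its positives. Nothing in the design makes the two agree, and the planned model has no term to absorb a difference. Antibiotic use and other enteric pathogens are both key variables in SAP 6.2 and could plausibly differ between the two windows. Part of such a calendar difference could then appear as a risk-factor effect, or hide one.

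Outcomes share the exposure to calendar time. Six months of follow-up from a June/July sample and from an October/November sample cover different parts of the year. Mortality at 30 days and 6 months is the primary outcome measure in Protocol 3.2.2.

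**Working it through.** **The plan's own figures.** From SAP Table 1: 103 + 71 + 39 = 213 cases; 365 + 147 = 512 controls; 213 + 512 = 725; 512/213 = 2.40. These agree with the stated totals and the 1:2.4 ratio. No count by round is given anywhere, so everything below on round rests on assumed ranges.

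**Chance imbalance.** If half of all samples come from each round, the standard error of the case-control difference in round share is √[0.25 × (1/213 + 1/512)] = 0.041. The 95% range is ±1.96 × 0.041, about ±8 percentage points, even with no systematic difference.

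**Size of the bias.** Call the two rounds A and B. Assume that 50% of controls and 50-70% of cases come from A, that control exposure averages 45% (the antibiotic figure in SAP section 3), and that it is 0-20 points lower in A. With no true effect, cases and controls have the same exposure within each round, and:

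- case exposure = s × p_A + (1 − s) × p_B, where s is the cases' share in A;
- crude OR = [case exposure / (1 − case exposure)] ÷ (0.45/0.55).

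Middle case: 0.6 × 0.40 + 0.4 × 0.50 = 0.44, so OR = (0.44/0.56) ÷ (0.45/0.55) = 0.96. Extreme case: 0.7 × 0.35 + 0.3 × 0.55 = 0.41, so OR = (0.41/0.59) ÷ (0.45/0.55) = 0.85. With the direction reversed, the extreme is 0.3 × 0.35 + 0.7 × 0.55 = 0.49, so OR = (0.49/0.51) ÷ (0.45/0.55) = 1.17.

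For a real effect, SAP section 3 gives 67% v 45%, an OR of (0.67/0.33) ÷ (0.45/0.55) = 2.48. Applying 2.48 within each round and then ignoring round gives the fourth column. The last column is the standard error of the log OR with round in the model, divided by that without it (213 cases, 512 controls, no other covariates).

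| Cases in A (controls 50%) | Control exposure A / B | Null OR reads as | True 2.48 reads as | SE ratio |
|---|---|---|---|---|
| 50% | 35% / 55% | 1.00 | 2.39 | 1.022 |
| 60% | 45% / 45% | 1.00 | 2.48 | 1.004 |
| 60% | 40% / 50% | 0.96 | 2.36 | 1.013 |
| 60% | 35% / 55% | 0.92 | 2.21 | 1.033 |
| 70% | 40% / 50% | 0.92 | 2.27 | 1.028 |
| 70% | 35% / 55% | 0.85 | 2.05 | 1.050 |

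The first two rows show that a null OR stays at 1.00 when either condition fails. The 2.39 in the first row reflects the non-collapsibility of the odds ratio; it is not confounding.

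**Why offering round to the selection is not enough.** The SAP states no entry threshold; assume p < 0.05. With 213 cases and 512 controls, round would enter about 23% of the time at a 5-point imbalance and 69% at 10 points. In an age group of about one third of the sample (assumed 71 cases, 171 controls), the figures are 11% and 29%. An imbalance large enough to move an estimate would often go unadjusted.

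**The case against.** The strongest reply is that no confounding has been shown. Controls are a random draw from the site's negatives, so the round split differs systematically only if positivity differs between rounds, and no such difference is reported. This stands, and it limits the point to a conditional one. Chance imbalance remains possible.

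A reader might infer that summer cases are in fact set against winter controls. The documents do not establish that. The Protocol's invitation letter has clinical data collected six months after each sampling date, which fits selection round by round. No section says that controls were drawn that way, and the SAP names location as the only matching factor.

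A reader might also picture a full winter-summer contrast. Winter is only the label in SAP 2.4; the months in SAP 6.3 are June/July and October/November. On those months, the 12-week look-back for antibiotics and proton pump inhibitors runs from about early March to July and from about early July to November, so it misses December to February. A large seasonal gap in antibiotic use is therefore not supported by the design. The reply covers less of the healthcare-contact item (2.6): its six-month look-back from a June sample reaches December.

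Finally, the SAP explains that the cohort is too small for closer matching. That is a fair reason not to match on round, since Table 1 notes sites with fewer than three controls per case. It is not a reason to leave round out of the model.

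**Conclusion.** The point holds as a minor one. The text supports two facts: location is the only matching factor, and neither sample date nor round has a role in the analysis. Whether the estimates are biased depends on two things the documents do not report: different round splits in cases and controls, and exposures that differ between rounds. It would go too far to say that season has distorted the results, or in which direction.

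Under the assumed ranges, a null OR reads as 0.85-1.00 (up to 1.17 in the reverse direction). The middle case, 0.96, is small beside effects of the size the SAP cites from earlier work. Nor is adjustment free. It costs one degree of freedom per model and about 0-5% in standard error, and small models feel this most: case category 3 has 39 cases, 15 of them in the community, before any split by age.

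**What to change.** - **SAP 6.3:** first reconcile the index dates. October/November 2019 lies outside the stated study period of June 2018 to June 2019 and disagrees with SAP 2.4. Protocol 2.4.2 gives May/June and October 2018. Round cannot be derived safely until this is settled.
- **Appendix 1, item 1.3:** define a binary variable, sampling round, derived from each patient's actual sample date, and give it an analysis role.
- **SAP 7.3:** state that round is included in every case/control logistic regression as a fixed covariate, and that forward selection applies only to the remaining variables.
- **Outcomes:** SAP 7.3 specifies a regression only for case/control status. If any adjusted outcome comparison is run, include round there too.
- **SAP 7.1:** tabulate cases and controls by round, which shows directly whether the first condition for confounding is met.

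No new data are needed, because the sample date is already collected. In the smallest age-group or case-category models the sponsor may prefer to show estimates with and without the term.
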